5 STATISTICAL METHODS/ANALYSES

The statistical analyses will be performed in accordance with ICH E9 guideline and guidelines presented in section 8.

SP will perform the statistical analysis of the efficacy, safety and PK/PD concentration data.

5.1 General Considerations

All statistical analyses will be performed using the Statistical Analysis System® software version 9.4 (or higher if available).

5.1.1 *Outputs Presentation*

5.1.1.1 *Tables Header*

Depending on the type of data, the summary tables will be presented as follows:

- For disposition, demographic and baseline data: by treatment group,
- For efficacy and safety data: by treatment group.

5.1.1.2 *Presentation of Treatment Group*

Tables, Figures and Listings (TFLs) will be displayed using the following treatment group label:
Triptorelin 6M

5.1.1.3 *Presentation of Visits / Timepoints*

Summaries by visit will be presented using visit number as collected in the Electronic Case Report Form (eCRF).

Visits in the TFLs will be presented as follows and in the following order:

Long Visit Name	Short Name
Screening	Scr
Baseline	Bsl
Day 1	D1
Day 2	D2
Day 3	D3
Day 5	D5
Day 8	D8
Day 15	D15
Day 22	D22
Week 4 Day 29	W4D29
Week 8 Day57	W8D57
Week 12 Day85	W12D85
Week 16 Day113	W16D113
Week 20 Day141	W20D141
End of Study/Early Withdrawal	EoS/EW

In the event a participant is enrolled, but does not receive study intervention, the participant will not remain in the study and EoS/EW assessment will not be performed.

5.1.2 *Descriptive Statistics*

All raw and derived variables will be listed and described using summary statistics. For categorical variables, summary statistics will be displayed using descriptive statistics by frequency count and percentages by category. The missing category will be presented if there is at least one missing category for at least one treatment group. Except otherwise specified, participants with missing data will be included in the calculation of percentages. For quantitative variables, summary statistics will be displayed using descriptive statistics by number of observations, mean, standard deviation (SD), median, minimum and maximum. Frequency and proportion of missing data will be displayed.

5.1.3 *Baseline Value*

Unless otherwise specified, baseline is defined as the last non-missing measurement taken prior to first Investigational Medicinal Product (IMP) administration (including unscheduled assessments).

5.1.4 *Reference Start Date and Study Day*

Reference start date is defined as the day of the first IMP administration.

The day of the first IMP administration will be Day 1. Study day will be calculated as:

- The difference between the event date and the reference date plus one day, if the event is on or after the reference date.

- The difference between the event date and the reference date, if the date of event is prior to the reference date.

Study day will appear in any listings where an assessment date or event date appears.

In case of partial or missing event date, study day will appear missing while any associated durations will be presented based on the imputations described in appendix [A2](#).

5.2 Randomisation, Disposition and Analysis Sets

Following disposition summaries and listings will be provided:

- Summary table with the number and percentages of screened and screen failure participants per centre on the screened set,
- Summary table with the number and percentage of participants screened, screen failed, reason for screen failures, treated, completer, withdrawn and reason for withdrawal, on the screened set,
- Summary table with the number and percentage of participants per visit for all participants enrolled,
- Summary table on duration of participant participation in the study. The definition of the duration of participant participation is from the date of initial consent to the date of end of study for all participants enrolled,
- Listing of dates of visit including study day (see section [5.1.4](#)) for all participants enrolled,
- Listing of screen failure participants on the screened set,
- Listing of withdrawal participants for all enrolled participants who meet all eligibility criteria.
- Listing of participants not meeting at least one inclusion criteria and/or fulfilling at least one exclusion criteria on the screened set,
- Summary of the number and percentage of participants in each analysis set by centre, treatment group, based on all participants enrolled with reasons for exclusion from each analysis set,
- Listing including flag for each analysis set and reason for exclusion from each set on all participants enrolled.

5.3 Protocol Deviations

An exhaustive list of major protocol deviations that may occur during the course of the study and any action to be taken regarding exclusion of participants from the PPS is defined in Protocol Deviation Specification. Major protocol deviations will be determined before database lock of the study, finalised during the blind data review and documented in a separate document data review report.

Following protocol deviation summary and listing will be provided for all participants enrolled:

- Number and percentage of participants with major protocol deviations by deviation category (see DV section of Standard Study Data Tabulation Model (SDTM) user guide).
- A listing of major protocol deviations.
- A listing of all protocol deviations.

Visits impacted by the pandemic will also be summarized and listed.

5.4 Demography and Other baseline characteristics

All demographic and baseline characteristics summaries will be provided for the FAS, PPS and safety set. Listing will be provided on all participants enrolled.

Following summaries will be provided on:

- Demographic variables (refer to appendix [A5](#) for EudraCT age categories),
- Other baseline characteristics (ECOG performance status, etc.),
- Disease characteristics (time since diagnosis [months], scan type [MRI, CT scan, Bone scan, other], scan location [prostate gland, pelvis, abdomen, chest, whole body, other], TNM stage of the disease, prior medication treatment for disease [Yes/No], Prior Radiotherapy for disease [Yes/No], Prior Surgical Procedures for disease [Yes/No]),

Time since diagnosis (months) = (Date of informed consent form - Date of histological diagnosis + 1) / 365.25*12. For participants who only have a year of the histological diagnosis date, the date of January 1 will be assumed. For participants who have both the year and month of the diagnosis date, the first date of diagnosis (01Mmmmyyyy) will be assumed.

Listings will also be provided for all the summaries listed above.

5.5 Medical history, non-drug therapies, medications and surgical procedures

Medical and surgical history, non-drug therapies and surgical procedures will be coded using the latest version of Medical Dictionary for Regulatory Activities (MedDRA) in effect within IPSEN at the time of database lock. Medications will be coded using the latest version of World Health Organization-Drug dictionary (WHODRUG) in effect within IPSEN at the time of database lock.

Medication, non-drug therapies and surgical procedures start and stop dates will be compared to the date of the first IMP administration to allow classification as either Prior only, Prior and Concomitant, or Concomitant only:

Prior (P)	Start and stop dates prior to the date of the first IMP administration.
Prior and Concomitant (PC)	Start date before the date of the first IMP administration and stop date on or after the date of the first IMP administration.
Concomitant (C)	Start date on or after the date of first IMP administration.

Summary tables on prior medications/non-drug therapies/surgical procedures will include “P” only, summary tables on concomitant medications/non-drug therapies/surgical procedures will include “C” and “PC”.

See detailed rules in appendix [A2](#) for classification of prior and concomitant medication/non-drug therapies, surgical procedures in case of partial/missing date.

Following summaries, presenting count and percentages of participants will be provided on the Safety Set:

- Significant medical and surgical history by primary system organ class (SOC) and preferred term (PT),
- Prior medications (P) for the study indication by ATC class and preferred Name (PN) (ATC level 2),
- Concomitant medications (PC, C) for the study indication by ATC class and preferred Name (ATC level 2),
- Prior surgical procedures (P) for the study indication by primary SOC and PT,

- Prior radiotherapies (P) for the study indication by primary SOC and PT,
- Prior medications (P) by ATC class and PN (ATC level 2),
- Concomitant medications (PC, C) by ATC class and PN (ATC level 2),
- Prior non-drug therapies (P) by primary SOC and PT,
- Concomitant non-drug therapies (PC, C) by primary SOC and PT,
- Concomitant surgical procedures (PC, C) by primary SOC and PT,

Listings will be provided for all the summaries listed above on all participants enrolled. These listings except medical and surgical history should include a flag indicating the category (P, PC, C) as described in the table above.

5.6 Compliance

Treatment compliance summary will be provided on the Safety Set, presenting count and percentages of participants who have administered all planned dose of Triptorelin.

5.7 Efficacy

5.7.1 General Considerations

The FAS and PPS will be used for efficacy analyses unless explicitly stated differently. Analysis on the FAS will be the primary analysis.

A listing of all efficacy data (raw and derived) will be provided (see listing detail conventions in Appendix A4). Descriptive statistics will be provided for all endpoints.

5.7.1.1 Significance Testing and Estimations

The statistical analysis of efficacy and safety is only descriptive therefore no formal statistical significance testing will be performed.

5.7.1.2 Handling of Dropouts and missing data

Diligent attempts will be made to limit the amount of missing data and to follow-up all treated participants to collect the primary and secondary efficacy endpoints for the statistical analysis. Unless otherwise specified, missing data will not be imputed. But for analysis of the percentage of participants maintaining castration levels of testosterone, specific handling rules of missing data are described in section 5.7.2.1.

5.7.1.3 Statistical/analytical issues

Adjustments for Covariates

This is a single-arm study, and no statistical comparisons will be performed, so covariates adjustment is not required.

Interim Analyses and Data Monitoring

Please refer to section 3.

Multicentre Studies

This is a multicentre study conducted in China.

Multiple Comparisons/Multiplicity

No multiple testing will be performed in this study because this is a single-arm descriptive safety and efficacy study.

Active-Control Studies Intended to Show Equivalence (if applicable)

Not applicable.

5.7.2 *Analysis of Primary Efficacy Endpoint*

5.7.2.1 *Endpoint, Treatment Effect and Estimand Definition*

The co-primary endpoints of efficacy are

- To determine the percentage of participants achieving castrate levels of serum testosterone (<50 ng/dL or 1.735 nmol/L) on Day 29 ± 3 days (Week 4) and
- To determine the percentage of participants maintaining the castrate levels of serum testosterone (<50 ng/dL or 1.735 nmol/L) from Week 8 (Day 57 ± 3 days) to Week 24 (Day 169 ± 3 days).

Percentage of participants achieving castrate levels of serum testosterone on Day 29

The percentage of participants achieving castrate levels of serum testosterone on Day 29 will be obtained as the number of participants achieving castrate levels on Day 29, divided by the number of participants in the FAS. The formula is

$$\text{Percentage} = \frac{\text{Number of participants achieving castrate levels on Day 29}}{\text{Number of participants in the analysis set}} \times 100$$

Percentage of participants maintaining castrate levels from Week 8 to Week 24

Percentage of participants maintaining castrate levels of serum testosterone from Week 8 to Week 24 for the FAS will be calculated as the number of participants achieving castrate levels of serum testosterone at all visits from Week 8 to Week 24, divided by the number of assessable participants in the analysis set. The formula is

$$\text{Percentage} = \frac{\text{Number of participants maintaining castrate levels from Week 8 to Week 24}}{\text{Number of assessable participants in the analysis set}} \times 100$$

To derive the percentage of participants maintaining castration levels of testosterone, missing data between Week 8 and Week 24 will be handled as follows:

- (a) In participants escaping castration at a certain visit (The escape event is defined as participant with a testosterone level >50 ng/dL), subsequent missing data is irrelevant; that is to say, participant will be treated as failure in that case.
- (b) Participants maintaining castration up to a certain visit with missing data afterwards (drop-out due to non-drug-related reasons) will be excluded from the analysis.
- (c) Participants maintaining castration up to a certain visit with missing data afterwards (drop-out due to drug-related reason) will be treated as having escaped castration (failure). Drug-related reason for drop-out is drug-related adverse event or death.
- (d) Missing data at 1 or more visit(s) between two visits where castration levels are maintained will be handled as missing for that particular visit, and the participant will be considered to have maintained castration if all visits with available results are maintained.

To derive the percentage of participants maintaining castrate levels of testosterone, assessable participants are defined as the number of participants having values at all visits and all participants having missing data according to the criteria a), c) and d) mentioned above. Participants having missing data according to the criteria b) will be excluded from this calculation. Participants who discontinue before Week 8 will also be excluded from this calculation.

Because this is a descriptive post-approval commitment study, and the protocol was approved before National Medical Products Administration (NMPA) implementation of ICH E9 (R1), estimands will not be considered for this study.

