9.4.1.3 Statistical/Analytical Methods

Statistical analyses will be performed by an external CRO, managed by the sponsor's Biometry department.

Demographic and Other Baseline Characteristics

Descriptive summary statistics (n, mean, standard deviation (SD), median, minimum, maximum) or frequency counts of demographic and baseline data (medical history, concomitant disease (predosing AEs and ongoing medical history, prior medications and therapies, etc.) will be presented for the FAS, PP and safety sets.

Participant Disposition and Withdrawals

The numbers and percentages of participants screened and included in each of the populations will be tabulated overall and by centre. The reasons for participant exclusions from each of the populations will also be tabulated. Primary reasons for discontinuation of study will be tabulated.

Adjustment for Country/Centre Effects

Descriptive analysis will be carried out to evaluate any possible centre effect.

9.4.2 *Analysis of Primary Endpoints*

The co-primary efficacy variables are

- percentage of participants achieving castrate levels of serum testosterone (<50 ng/dL or 1.735 nmol/L) and
- percentage of participants maintaining the castrate levels from Week 8 to Week 24.

The percentage of participants achieving castrate levels of serum testosterone (<50 ng/dL or 1.735 nmol/L) on Day 29 will be obtained as the number of participants with castrate levels at the visit, divided by the total number of participants on Day 29 in the considered population.

Percentage of participants maintaining the castrate levels of serum testosterone (<50 ng/dL or 1.735 nmol/L) from Week 8 to Week 24 will be calculated as the number of participants with castrate levels at all visits from Week 8 to Week 24, divided by the total number of assessable participants.

To derive the percentage of participants maintaining castration levels of testosterone, missing data will be handled as follows:

- (a) In participants escaping castration at a certain visit, subsequent missing data is irrelevant.
- (b) Participants maintaining castration up to a certain visit with missing data afterwards (drop-out due to non-drug-related reasons) will be excluded from the analysis.
- (c) Participants maintaining castration up to a certain visit with missing data afterwards (drop-out due to drug-related reasons) will be treated as having escaped castration (failure).

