2.6 Change from Statistical Section of the Protocol

Protocol	SAP
Section 9.4.1.3 Demographic and Other Baseline Characteristics Descriptive summary statistics (n, mean, standard deviation (SD), median, minimum, maximum) or frequency counts of demographic and baseline data (medical history, concomitant disease (predosing AEs and ongoing medical history, prior medications and therapies, etc.) will be presented for the FAS, PP and safety sets.	Section 5.5 Medical history, non-drug therapies, medications and surgical procedures will be present for only Safety Set.

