4 ANALYSIS SETS

Screened Set

The screened set will contain all participants screened (i.e. who signed the informed consent).

Full Analysis Set (FAS)

The FAS will contain all treated participants who complete the study or is a treatment failure. Completing the study is defined as having serum testosterone measurement at baseline, Day 29 and Day 169. Treatment failure is defined as escaping castration (testosterone level ≥ 50 ng/dL or 1.735 nmol/L) at any assessments on and after Day 29 during the study, or premature discontinuation from the intervention period due to drug-related reasons (adverse event or death).

Per Protocol Set (PPS)

The PPS will contain all participants in the FAS who have no impacting major protocol deviations (i.e. that could potentially affect the primary efficacy endpoint outcome for the participant) as described in the protocol deviations document.

Safety Set

The safety set will contain all participants who receive the single dose of study intervention.

Rich PK Analysis Set (for non-compartmental analysis)

The rich PK analysis set will contain all participants in the PK/PD subset who receive one dose of study intervention, have no major protocol deviations affecting the PK variables, and who have a sufficient number of plasma concentrations to estimate the main PK parameters (maximum observed plasma drug concentration (C_{max}), time to maximum observed drug concentration (t_{max}) and area under the plasma concentration time curve (AUC)).

The criteria of major protocol deviations affecting the PK variables will be defined in the protocol deviation document. The process to review major protocol deviations potential impact on PK parameters will be ongoing and the final Rich PK Analysis Set will be determined during data review meeting.

Population PK Analysis Set

The population PK analysis set will contain all participants who received one dose of triptorelin and who have at least one triptorelin plasma concentration and no major protocol deviations affecting PK variables.

Rich PD Analysis Set

The rich PD analysis set will contain all participants in the PK/PD subset who have a sufficient number of PD (testosterone) measurements to estimate the main PD parameters (maximum observed concentration (C_{max}), time to maximum observed concentration (t_{max}) and time to castration (t_{castr})).

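### The Day 29 co-primary is divided by a FAS that depends on events after Day 29, and no planned analysis gives a Day 29 percentage with a confidence interval outside the FAS or PPS

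*SAP*

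**What the plan says.** SAP 5.7.2.1 takes the Day 29 percentage as the "number of participants achieving castrate levels on Day 29, divided by the number of participants in the FAS". SAP 5.7.1 adds: "Analysis on the FAS will be the primary analysis".

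SAP 4, matching protocol 9.3, defines the set: "The FAS will contain all treated participants who complete the study or is a treatment failure". On completion it says: "Completing the study is defined as having serum testosterone measurement at baseline, Day 29 and Day 169". Treatment failure means testosterone at or above 50 ng/dL at any assessment from Day 29 on, or stopping early for a drug-related adverse event or death.

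SAP 5.7.2.3 repeats the Day 29 analysis once, on the PPS, which is a subset of the FAS. Sensitivity analyses 2 to 5 are defined only for maintenance from Week 8 to Week 24. Among them, analysis 3 uses a wider treated population.

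Protocol 9.4.2 words the Day 29 denominator differently: the number castrate at the visit is "divided by the total number of participants on Day 29 in the considered population". SAP 2.6 lists one change from the protocol, on another matter: "Medical history, non-drug therapies, medications and surgical procedures will be present for only Safety Set".

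**The concern.** The Day 29 result is known on Day 29. Whether a man counts towards it can be decided up to 20 weeks later (Day 169 minus Day 29 is 140 days). The rule does not treat outcomes alike. A measured Day 29 failure is always in. A Day 29 success can be removed by a missing Day 169 sample. A man without a Day 29 value cannot be a completer, so he is out unless he later escapes or stops for a drug-related reason.

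These exclusions act in opposite directions. Removing known successes lowers the percentage. Removing men with no Day 29 value raises it relative to an analysis that keeps every treated man and counts the missing as not achieving. No test is planned, so the estimate and its interval are the Day 29 result, and a reader needs to know which men it describes.

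**Working it through.** **The plan's own figures.** Inputs from SAP 2.3: null 85%, two-sided 0.05, n = 165, true rates 93% and 97.5%, dropout about 15%, N = 195. With 0.025 in the upper tail, the exact test needs at least 150 of 165. Power is 88.3% at 93% and above 99.9% at 97.5%. 165/0.85 = 194.1, rounded up to 195. All the stated figures reproduce.

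**Effect 1: known successes removed.** Let p be the true Day 29 rate and d the share of Day 29 successes dropped for want of a Day 169 value. All measured failures stay, so the expected percentage is p(1 − d) / [p(1 − d) + 1 − p]. With p = 0.975 (the planning value):

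- d = 0.05: 97.4%, a shift of 0.13 points
- d = 0.10: 97.2%, a shift of 0.27 points
- d = 0.15: 97.1%, a shift of 0.43 points

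**Effect 2: men with no Day 29 value removed.** Assumptions: 195 treated; 29 dropouts (15% of 195 is 29.25), all non-drug-related and without escape; 5 measured Day 29 failures; everyone else has Day 29 and Day 169 values. Let k of the 29 leave before Day 29.

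- FAS: (195 − 29 − 5)/(195 − 29) = 161/166 = 97.0% (95% CI 93.1 to 99.0) for every k
- Men with a Day 29 value: (190 − k)/(195 − k)
- All treated, missing counted as not achieving: (190 − k)/195

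| k | Men with a Day 29 value | All treated, missing = not achieving (Clopper-Pearson 95% CI) |
|---|---|---|
| 0 | 190/195 = 97.4% | 190/195 = 97.4% (94.1 to 99.2) |
| 3 | 187/192 = 97.4% | 187/195 = 95.9% (92.1 to 98.2) |
| 6 | 184/189 = 97.4% | 184/195 = 94.4% (90.1 to 97.2) |
| 10 | 180/185 = 97.3% | 180/195 = 92.3% (87.6 to 95.6) |
| 15 | 175/180 = 97.2% | 175/195 = 89.7% (84.6 to 93.6) |

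The FAS figure is the same in every row. The documents give neither the timing nor the cause of dropout, so the table shows a range and is not a forecast.

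**Denominator.** Every completer has a Day 29 value. The protocol and SAP denominators therefore differ only for treatment failures in the FAS who have none. Suppose 167 men in the FAS have a Day 29 value and 162 of them are castrate. Protocol 9.4.2 gives 162/167 = 97.0%. With 1, 2 or 3 such failures the SAP gives 162/168 = 96.4%, 162/169 = 95.9% or 162/170 = 95.3%, about 0.6 points per man.

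**The case against.** **The information is not hidden.** This largely stands. SAP 5.2 plans participant counts per visit and reasons for exclusion from each analysis set. SAP 5.7.2.2 plans castration achieved, Yes or No, by visit, and SAP 5.1.2 adds a missing category. Every man measured at or above 50 ng/dL on Day 29 is in the FAS, so Day 29 attendees minus the FAS No results gives the number of achievers among all treated men. With k = 10 that is 185 − 5 = 180. The reconstruction assumes that every attendee was sampled, and it yields no reported percentage or interval. A reader might infer that the plan conceals these men. It does not, and SAP 5.7.2.2 also lists testosterone values for everyone enrolled.

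**The size depends on the comparator.** This also stands. Against measured values the shift is at most 0.4 points and conservative. The larger gaps appear only when missing counts as failure, which is a bound and not an efficacy estimate. A reader might infer that the FAS inflates the Day 29 rate. The documents do not support that, because they fix neither the net direction nor the number of early leavers. They also do not show that most men without a Day 29 value fall outside the FAS; that would be an inference about why men leave.

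**The study is descriptive.** No test is planned, SAP 5.7.2.1 sets estimands aside, and leaving non-drug dropouts out matches the rule for the maintenance endpoint. This rules out any claim about power or error rates. It does not settle which men the reported percentage describes.

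**Follow-up is already planned.** SAP 5.7.1.2 promises diligent attempts "to follow-up all treated participants to collect the primary and secondary efficacy endpoints for the statistical analysis". That is an intention and does not guarantee that the values will exist. For men who leave before Day 29 they will not.

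**Conclusion.** The point holds in limited form. The FAS selects on events after Day 29, and the only repeat of the Day 29 analysis is on a narrower set. The effect against measured values is 0.1 to 0.4 points downward, if 5% to 15% of successes are dropped and the true rate is 97.5%. Against all treated men with missing counted as not achieving, the FAS figure runs from 0.4 points too low (k = 0) to 7.3 points too high (k = 15) in the cases tabulated. Those cases rest on 29 non-drug dropouts, 5 measured failures and an assumed split of timing. Sample size is not affected.

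The denominator mismatch is a separate, minor inconsistency of about 0.6 points per affected man. It should be recorded. The whole point is a cheap improvement in reporting and no reason to replace the primary analysis.

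**What to change.** Keep the FAS analysis as primary. Before database lock, add to SAP 5.7.2.3 two Day 29 percentages with Clopper-Pearson 95% CIs:

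1. All treated participants with a Day 29 testosterone value, with no Day 169 requirement. This set is not strictly wider than the FAS, because it omits treatment failures with no Day 29 value. The table should say so.
2. The Safety Set, with a missing Day 29 value counted as not achieving, labelled as a lower bound and not as the efficacy estimate.

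Reconcile the Day 29 denominator between protocol 9.4.2 and SAP 5.7.2.1, or list the difference in SAP 2.6.

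Do not add a Day 169 ± 3 days condition for entry to the FAS. SAP 6.1 says that analyses need no visit windows unless otherwise specified, and such a condition would remove more known Day 29 successes.

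The cost is two tables and a few lines of SAP text, with no new data. The drawback is that analysis 2 counts men missing for unrelated reasons as not achieving, so its label matters. Under SAP 1, deviations from the SAP after database lock have to be documented in the CSR, which is why this is better done before then.
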